8.1.1 All patients

- Histological confirmation of primary breast, prostate or NSCLC*
- Complete medical history
- Physical examination including WHO performance status, body weight, height, blood pressure
- Negative pregnancy test (for women of childbearing potential)
- Baseline tumour assessment.

* Will be before 42 days prior to randomisation

The following are required to evaluate if patients are suitable for SBRT to the relevant metastatic subsite:

8.1.2 Liver/ Spine/ Lung metastases/Bone metastases

| | |
|------------------|--|
| Liver metastases | 
 Clotting screen (INR), liver function (ALT/AST, bilirubin, albumin) to ascertain sufficient organ function to enable SBRT. A DimercaptoSuccinic Acid (DMSA) scan or equivalent may be required as per local guidelines if the renal radiation dose is likely to be significant. |
| Spine metastases | 
 MRI whole spine. |
| Lung metastases | 
 Pulmonary function tests to include FEV 1, FVC, and TLCO/KCO. Follow up pulmonary function tests if clinically indicated. |
| Bone metastases | 
 Bone lesions defined as non-measurable via RECIST v1.1 should still be assessed at baseline if the lesion(s) is a visible, image definable target suitable for SBRT planning and delivery. |

8.1.3 Breast primary site

- CT scans of the chest, abdomen and pelvis. Scans may be replaced by FDG PET-CT scan (as long as the CT scan is of diagnostic quality), or whole body dwMRI if locally available.
- Baseline measure of tumour marker Ca 15-3 (where locally available)

8.1.4 NSCLC primary site

- Patients in the SBRT + SOC group will need to stop tyrosine kinase inhibitor (TKI) treatment **at least one day and up to one week prior** to commencing SBRT. Patients can recommence TKI treatment one day after receiving their last fraction.
- CT scans of the chest, abdomen and pelvis. Scans may be replaced by FDG PET/CT scan (as long as the CT scan is of diagnostic quality).
- CT brain with contrast or MRI brain with contrast to exclude intracranial disease.

8.1.5 Prostate primary site:

- Bone scan and CT scans of the chest, abdomen and pelvis. These scans may be replaced by choline or PSMA PET/CT scan (as long as the CT scan is of diagnostic quality), or by whole body dwMRI if locally available
- PSA and testosterone.

8.2 Pre-Treatment assessments

The following assessments should be conducted once patient eligibility has been confirmed:

- Full blood count, urea and electrolytes, LFTs (and clotting screen (INR) for patients with liver metastases)
- Assessment of baseline symptoms using NCI CTCAE v.4.0 and RTOG and concomitant medications taken from 30 days prior to randomisation
- Baseline quality of life questionnaire (EORTC QLQ C30 and EQ5D) (should be before treatment allocation is known to the patient).

8.3 Follow-up assessments

8.3.1 End of Treatment – All patients

The following assessments should be conducted within +/- 7 days of the last fraction of SBRT visit or within 6 weeks after randomisation for patients randomised to SOC only.

- Directed physical examination including WHO performance status, weight and height.
- Assessment of acute toxicity using NCI CTCAE v.4.0 and concomitant medications
- Quality of life questionnaire (EORTC QLQ C30 and EQ5D).

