3 TRIAL DESIGN

CORE is a phase II/III, multi-centre, non-blinded, parallel group randomised controlled trial in patients with breast, prostate or NSCLC primary cancer comparing standard of care (SOC) with or without SBRT for extra-cranial metastases. The aim of the phase II study is to demonstrate 1) feasibility of recruitment, 2) deliverability of the study in a multi-centre setting and 3) activity of SBRT, based on progression free survival, across the three tumour types. If all three aims are achieved the trial will be amended to roll into parallel tumour-site specific phase III trials.

Eligible patients are those with either primary breast, prostate or NSCLC who have presented with ≤ 3 extra-cranial, metachronous, oligometastases, all suitable for SBRT. Patients will be randomised in a 1:1 ratio to either SOC or SOC with the addition of SBRT. Choice of SOC treatment is at the discretion of the local oncologist and defined per patient prior to randomisation (see Section 9 Trial Treatment). Patients randomised to SBRT+SOC will receive a dose and fractionation regimen dependent on the metastatic site and proximity to dose limiting organs and normal tissues. Treatment will take place within 6 weeks of randomisation. The average scheme would be 3 treatments over 5 days but the maximum period of SBRT duration could be 8 treatments over 19 days.

All patients will be reviewed every 3 months with a clinical examination and tumour markers (where applicable) during years 1 and 2, and 6 monthly thereafter to 5 years. Staging and follow up imaging protocols will be tumour type dependent:

- **Breast:** 3 monthly CT scans for years 1 and 2, and 6 monthly thereafter to 5 years.
- **NSCLC:** 3 monthly CT scans for years 1 and 2, 6 monthly to year 3, then annually to 5 years.
- **Prostate:** CT scans will be performed at 6, 12 and 24 months with imaging triggered by appropriate PSA rises. A rising PSA defined as 2 successive PSA rises from nadir, measured a minimum of 4 weeks apart, will be used to trigger additional imaging (CT) between these time points.

All patients will have a toxicity assessment at each clinic visit and patient reported quality of life (QOL) assessment at 3, 6, 12, 18 and 24 months.

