8.8 Schedule of assessments

| Visit/Assessments/ Procedures | Pre-randomisation | Pre-treatment | End of trial treatment for SBRT + SOC group or equivalent for SOC group | Time from randomisation | | | | | | | | | | | | | |
|--|-------------------|---------------------------------------|---|-------------------------|-----|------------------|------|------------------|------------------|------------------|------|------------------|------------------|----------------|------------------|----------------|------------------|
| | Within 42 days | Following confirmation of eligibility | SBRT + SOC group: within +/- 7days of last SBRT treatment SOC only group: within 6 weeks after randomisation | 3 M | 6 M | 9 M | 12 M | 15 M | 18 M | 21 M | 24 M | 30 M | 36 M | 42 M | 48 M | 54 M | 60 M |
| Informed consent | X | | | | | | | | | | | | | | | | |
| Histological confirmation of primary breast, prostate or NSCLC | X* | | | | | | | | | | | | | | | | |
| Complete medical history | X | | | | | | | | | | | | | | | | |
| Physical examination including WHO performance status, body weight, height, blood pressure (BP at baseline only) | X | | X | X | X | X | X | X | X | X | X | X | X | X | X | X | X |
| Tumour primary assessment using RECIST v.1.1 criteria | X | | | X ^{B,L} | X | X ^{B,L} | X | X ^{B,L} | X ^{B,L} | X ^{B,L} | X | X ^{B,L} | X ^{B,L} | X ^B | X ^{B,L} | X ^B | X ^{B,L} |
| Concomitant therapy assessment | | X | X | | | | | | | | | | | | | | |
| Full blood count, urea and electrolytes, LFTs | | X | | | X | | | | | | | | | | | | |
| Pregnancy test (for women of childbearing potential) | X | | | | | | | | | | | | | | | | |
| Symptom assessment using NCI | | X | X | X | X | X | X | X | X | X | X | X | X | X | X | X | X |

| Visit/Assessments/ Procedures | Pre-randomisation | Pre-treatment | End of trial treatment for SBRT + SOC group or equivalent for SOC group | Time from randomisation | | | | | | | | | | | | | |
|---|-------------------|---------------------------------------|---|-------------------------|----------------|----------------|----------------|----------------|----------------|----------------|----------------|----------------|----------------|----------------|----------------|----------------|----------------|

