9.4 Concomitant therapy

All medication considered necessary for the patients' welfare and which is not expected to interfere with the evaluation of the treatment may be given at the discretion of the investigator. Prescription and over-the-

counter medications that the patient takes from 30 days prior to randomisation until the end of treatment visit (within +/- 7 days of the last fraction of SBRT or within 6 weeks after randomisation for patients randomised to SOC only) should be recorded on the eCRF.

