A4. QUALITY OF LIFE STUDY

Patient reported outcomes (PRO) are a key secondary endpoint within CORE.

A4.1 Quality of life measures

Patient reported outcomes will be measured using the EORTC QLQ C30 and the EQ-5D. Patients will complete the EORTC QLQ C30 general cancer questionnaire. Participants will also be asked to complete the EQ-5D questionnaire, a brief standardised instrument which provides a simple descriptive profile of their health status.

A4.2 Study design

Patients are eligible for the PRO study if they fulfil the CORE eligibility criteria. Participants will be asked in the patient information sheet to consent to regular completion of PRO questionnaires. Patients who decline to take part in the CORE PRO study will remain eligible for the main trial. PRO is a secondary endpoint in the main trial and the primary time point of interest is 12 and 18 months after completion of radiotherapy.

A4.3 Timing of data collection

Participants will be asked to complete a questionnaire in clinic within one week prior to randomisation and if this window is missed should be before treatment allocation is known to the patient (SOC or SBRT+ SOC). Questionnaires will be completed in clinic at the end of SBRT delivery/6 weeks from randomisation. Further booklets will be sent to participants' homes by ICR-CTSU at 3, 6, 12, 18 and 24 months from randomisation.

A4.4 Compliance

Missing data may hamper interpretation of PRO. Missing data may arise because participants do not complete the questionnaires at the appropriate time (unit non-response), or because patients may miss questions within the questionnaires (item non-response). During the study, compliance with PRO questionnaire completion will be monitored by the trial oversight committees.

A4.5 Statistical considerations

Patient reported outcome analyses will be used to supplement results of clinician assessed treatment toxicity; therefore a formal sample size calculation has not been performed. An analysis plan will be developed in consultation with the TMG with key endpoints identified from each questionnaire. Standard algorithms will be used to derive scores and handle missing data in quality of life questionnaires. Quality of life data will be presented at individual time-points and analyses to account for the longitudinal nature of the data may be used.

A5. EXPECTED SERIOUS ADVERSE EVENTS

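### The SBRT-arm end-of-treatment window opens 7 days before the last fraction, which for most short courses is before any SBRT has been given

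*Protocol*

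**What the plan says.** Three places fix the SBRT-arm visit. Section 8.3.1: "The following assessments should be conducted within +/- 7 days of the last fraction of SBRT visit or within 6 weeks after randomisation". The column head in section 8.8: "SBRT + SOC group: within +/- 7days of last SBRT treatment". Section 9.4, which uses the visit as the end of medication recording: "within +/- 7 days of the last fraction of SBRT or within 6 weeks after randomisation for patients randomised to SOC only". None requires SBRT to have started or finished.

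The visit collects a directed examination, the two QoL questionnaires and toxicity ("Assessment of acute toxicity using NCI CTCAE v.4.0 and concomitant medications"). Section 8.8 shows no other toxicity or QoL assessment between the pre-treatment assessments and month 3. It schedules concomitant therapy at only two points, pre-treatment and this visit.

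On course length, section 3 says: "The average scheme would be 3 treatments over 5 days", with a longest course of eight treatments in 19 days. Table 1 in section 9.1.4 lists nine regimens and gives each a maximum duration.

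On QoL timing, Appendix A4.3 says: "Questionnaires will be completed in clinic at the end of SBRT delivery/6 weeks from randomisation".

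**The concern.** A window symmetric around the last fraction works only if the course is longer than the backward half of the window. Here the typical course is shorter. A site can do the visit before the first fraction, or part-way through a longer course, and still comply with sections 8.3.1, 8.8 and 9.4. The questionnaire would then break Appendix A4.3.

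Section 11.2.4 summarises toxicity and QoL visit by visit. At this visit a pre-dose record is in effect a second baseline. Three things are exposed:

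- the end-of-treatment toxicity table;
- the end-of-treatment QoL description, which no later questionnaire can replace because the next is at month 3;
- medication taken during SBRT, because section 9.4 stops recording at this visit.

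**Working it through.** **Inputs.** Window: last fraction minus 7 to plus 7 days (8.3.1, 8.8, 9.4). Fractions, frequency and maximum duration: Table 1. Start on any day of the week: section 9.1.5. Assumptions: fractions fall on weekdays, a weekend slot moves to Monday, and durations count both the first and the last day.

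**Reproducing the protocol's own course lengths.** Three alternate-day fractions from a Monday fall on days 1, 3 and 5, which gives 5 days, as in section 3. Eight alternate-day fractions take 17 to 19 days over the five weekday starts. The 19 comes from a Thursday start and matches the stated maximum. The counting rule therefore agrees with the document.

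**Formula.** Window opening relative to first fraction = (course length in days − 1) − 7. A negative result means that the window opens before the first fraction.

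| Course | Length in days (Mon to Fri starts) | Opening relative to first fraction (days) |
|---|---|---|
| 3 fractions, alternate days | 5, 7, 6, 7, 6 | −3, −1, −2, −1, −2 |
| 3 fractions, daily (adrenal option) | 3, 3, 3, 5, 5 | −5, −5, −5, −3, −3 |
| 5 fractions, daily (liver option) | 5, 7, 7, 7, 7 | −3, −1, −1, −1, −1 |
| 5 fractions, alternate days | 10, 11, 10, 12, 11 | +2, +3, +2, +4, +3 |
| 8 fractions, alternate days | 17, 18, 17, 19, 18 | +9, +10, +9, +11, +10 |

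**At the Table 1 maxima.** A 7-day course gives (7 − 1) − 7 = −1. The five 3-fraction regimens with that cap (adrenal, liver, spine, bone, lymph node) therefore always have a window that opens before the first fraction. Lung in 3 fractions may run to 14 days, and (14 − 1) − 7 = +6, so it is affected on its alternate-day schedule but not if stretched that far.

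**Reach.** Five regimens always, plus 3-fraction lung on alternate days, plus 5-fraction liver given daily: 5 + 1 + 1 = 7 of the 9 regimens can have a pre-dose visit. For the alternate-day 5- and 8-fraction courses, and counting a fraction given on the opening day, 2 of 5 and 5 of 8 fractions have been delivered when the window opens. Those records can be partial-dose but not pre-dose.

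**What later data recover.** Section 10.3 asks for the highest grade since the last visit, and section 11.2.2 counts events up to 3 months as acute. The month 3 record therefore covers a course that an early visit missed. SBRT may start up to 6 weeks after randomisation (9.1.1). With 3 months taken as about 13 weeks and a course of about 1 week, recall from the last fraction is about 13 − 1 = 12 weeks for a start at once and 13 − 6 − 1 = 6 weeks for the latest start. No such rule covers end-of-treatment QoL or the medication record.

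**The case against.** The strongest reply is that intent is clear and little depends on the window. The visit is headed as end of treatment, sits among the follow-up assessments, and A4.3 points the same way, so few sites would hold it before treatment. Formal QoL comparisons are at 12 and 18 months. Section 3 does not list the end-of-treatment questionnaire among its QoL time points. Concomitant medication feeds no stated endpoint, and section 9.2.1 captures TKI dates and radiosensitiser use separately. Nearly all of this stands and limits the harm. It does not make the window right: three sections permit what A4.3 rules out, and an analysis plan cannot recover data that were never collected.

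Four stronger readings are tempting, and the document does not support them.

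- *SBRT will look better tolerated than it is.* The SOC-only visit may take place at any time up to 6 weeks after randomisation, while A4.3 puts it at 6 weeks. A near-baseline record is therefore possible in both arms, and the direction of any bias is open.
- *The acute toxicity comparison is understated.* The month 3 rule largely protects the grade 2 or higher comparison, subject to recall and to sections 8.3.2 to 8.3.4 labelling month 3 toxicity as late.
- *About half of the visits would come too early.* An even spread over the 15-day window puts 7/15 = 47% before the last fraction, but only 1/15 to 3/15 (7% to 20%) before the first fraction of a 3-fraction alternate-day course. Nothing in the protocol supports an even spread, so neither figure is a forecast.
- *Every 3-fraction course is affected.* Lung escapes if its course is stretched towards 14 days.

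**Conclusion.** The point holds as a badly fixed visit window and an internal contradiction, with a modest effect. On the protocol's own course lengths, a compliant visit can come before any SBRT in seven of the nine Table 1 regimens, and part-way through treatment on the alternate-day 5- and 8-fraction courses. What can be wrong is the descriptive end-of-treatment toxicity and QoL summaries and the completeness of the concomitant-medication record. PFS, the 12- and 18-month QoL comparisons and the safety guideline on late grade 4/5 toxicity are not affected.

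The result rests on the weekday and day-counting assumptions above and on a single course. Several lesions treated in sequence could make the overall course longer and remove the pre-dose period. How many visits would be early cannot be told from the protocol.

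**What to change.** In sections 8.3.1, 8.8 and 9.4, set the SBRT-arm window from the day of the last fraction to 7 days after it. Reconcile these sections with Appendix A4.3, including the SOC-only timing, where an upper limit of 6 weeks and a visit at 6 weeks are different rules. In the analysis, flag assessments dated before the last fraction, and leave those dated before the first fraction out of the end-of-treatment summaries.

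The cost is a wording change in a few places, a narrower visit window, and a few records not counted at that time point. A visit on the day of the last fraction complies, so no extra attendance is needed. No dose or treatment schedule changes.

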8.3.2 Breast Primary Patients

The following assessments should be conducted for all breast primary patients at each follow up visit (Months 3, 6, 9, 12, 15, 18, 21, 24, 30, 36, 42, 48, 54 and 60 months post randomisation):

- CT scan of chest, abdomen and pelvis. This may be replaced by FDG PET/CT scan as long as the CT scan is of diagnostic quality, or whole body dwMRI if locally available.
- Tumour assessment according to RECIST v.1.1 criteria, where possible. In instances where RECIST assessment is not possible assessment by other methods should be considered or a clinical assessment of widespread progression should be performed. Assessment of tumour marker Ca 15-3 (where locally available).
- Physical examination including WHO performance status, weight and height.
- Assessment of late toxicity using NCI CTCAE v.4.0 and RTOG (RTOG is excluded for the first 3 month post randomisation).

In addition the following assessments should be performed:

Month 6 post randomisation

- Full blood count, urea, electrolytes and LFTs (ALT/AST, bilirubin, albumin).

Months 3, 6, 12, 18 and 24 post randomisation

- Quality of life questionnaire (EORTC QLQ C30 and EQ5D)

8.3.3 NSCLC Primary patients

The following assessments should be conducted for all NSCLC primary patients at each follow up visit (Months 3, 6, 9, 12, 15, 18, 21, 24, 30, 36, 42, 48, 54 and 60 months post randomisation):

- Physical examination including WHO performance status, weight and height.

- Assessment of late toxicity using NCI CTCAE v.4.0 and RTOG (RTOG is excluded for the first 3 month post randomisation).

In addition the following assessments should be performed:

Months 3, 6, 9, 12, 15, 18, 21, 24, 30, 36, 48 and 60 months post randomisation

- CT scan of chest, abdomen and pelvis. This may be replaced by FDG PET/CT scan as long as the CT scan is of diagnostic quality.
- Tumour assessment according to RECIST v.1.1 criteria, where possible. In instances where RECIST assessment is not possible assessment by other methods should be considered or a clinical assessment of widespread progression should be performed.

Month 6 post randomisation

- Full blood count, urea, electrolytes and LFTs (ALT/AST, bilirubin, albumin).

Months 3, 6, 12, 18 and 24 post randomisation

- Quality of life questionnaire (EORTC QLQ C30 and EQ5D)

8.3.4 Prostate Primary patients

The following assessments should be conducted for all prostate primary patients at each follow up visit (Months 3, 6, 9, 12, 15, 18, 21, 24, 30, 36, 42, 48, 54 and 60 months post randomisation):

- Physical examination including WHO performance status, weight and height.
- Assessment of late toxicity using NCI CTCAE v.4.0 and RTOG (RTOG is excluded for 3 month post randomisation).
- Assessment of tumour marker PSA.

A rise in PSA levels may indicate the need for unscheduled bone and CT scan. Scans may be replaced by choline or PSMA PET/CT scan or whole body dwMRI if locally available. A rising PSA is defined as 2 successive PSA rises from nadir, measured a minimum of 4 weeks apart. If the overall PSA rise has a doubling time of ≥ 3 months or the PSA level has doubled the original PSA value at trial entry or if clinically indicated, then restaging should be considered. Where scanning has been indicated tumour assessment according to RECIST v1.1 criteria should be carried out, where possible.

In addition the following assessments should be performed:

6, 12 and 24 months after randomisation

- Bone and CT scan of chest, abdomen and pelvis. These may be replaced by choline or PSMA PET/CT or wb-dwMRI if locally available.
- Tumour assessment according to RECIST v.1.1 criteria, where possible. In instances where RECIST assessment is not possible assessment by other methods should be considered or a clinical assessment of widespread progression should be performed.

Month 6 post randomisation

- Full blood count, urea, electrolytes and LFTs (ALT/AST, bilirubin, albumin).

Months 3, 6, 12, 18 and 24 post randomisation

- Quality of life questionnaire (EORTC QLQ C30 and EQ5D)

Months 12, 24, 36, 48 and 60 post randomisation

- Assessment of testosterone

8.3.5 Liver metastases:

In addition to the assessments outlined for the primary tumour patients the following assessments should be performed for patients with liver metastases as indicated:

| | |
|-------------------------------|---|
| 3 months after randomisation | Clotting screen (INR) and liver function (ALT/AST, bilirubin, and albumin) to ascertain liver function status regarding radiation induced liver disease |
| 6 months after randomisation: | Clotting screen (INR). |
| 12 months after randomisation | Clotting screen (INR), liver function (ALT/AST, bilirubin and albumin) to ascertain liver function status regarding radiation induced liver disease |

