11.1.2 Sample size

This phase II screening study has been designed with a primary endpoint of PFS, and relaxed one-sided $\alpha=0.20$ and $\beta=0.20$ (13). The control arm PFS is estimated based on the expected contribution of each primary tumour site to the overall final sample size. Based on observed recruitment in the first year this is estimated at 75% prostate, 14% breast and 11% lung. Assuming a median PFS of 5 months for NSCLC, 12 months for breast and 18 months for prostate patients (14-22), it is estimated that the median PFS in the control group after randomisation will be 16 months. The phase II SABR-COMET trial targets a hazard ratio (HR) for OS of 0.6 (23). For CORE, a more conservative effect size has been chosen reflecting clinical opinion of what would constitute a PFS signal worthy of a phase III OS trial. In order to detect a HR of 0.75 for improvement of PFS i.e. extending the median cohort PFS by 4 months in the experimental arm with 80% power, a total of 230 patients are required (138 events). Assuming a 5% rate of patients lost to follow up at the point of data analysis, a total of 242 patients will be required (121 per treatment group). Dependent on observed rates of accrual this total may increase to a maximum of 270 to allow for each cohort to achieve a minimum of 50 patients. The sample size calculations, made using the *artsurv* command in Stata version 13, assume 50% recruited in both years 1 and 2 and 12 months of additional follow up.

The decision rule to proceed to phase III will be based on a 3 outcome design. An overall result significant at the 10% level would support continuation to phase III; significance between 10% and 20% would require supportive evidence from secondary endpoints with a particular emphasis on local tumour control and FFWMD. If the significance is >20% then the study will not progress to phase III unless there is clear

heterogeneity of outcomes between the 3 tumour subgroups supporting a signal in selected tumour sites in which case consideration would be given to progressing to an extended phase 2 evaluation for that tumour site alone.

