11.2 Endpoint definitions

11.2.1 Primary endpoint

Progression free survival is defined as time from randomisation to evidence of progression of cancer at any site or death from any cause.

Progression events should be imaging defined in all tumour types according to RECIST criteria. In addition, for prostate cancer patients progression by bone scan and PSA progression will be considered. On the rare occasions that progression cannot be measured by scan or biochemical failure (prostate only), clinical evidence of widespread progression will count as a PFS event.

Where SBRT specific consensus response assessment criteria exist for specific sites (e.g. spine), progression of SBRT treated lesions will be defined according to these guidelines.

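### The PSA rule for unscheduled restaging in prostate patients differs between sections, and its doubling-time limb, as written, is met by slow rises and missed by fast ones

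*Protocol*

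**What the plan says.** Protocol Section 3 schedules CT for prostate patients at 6, 12 and 24 months. It defines a rising PSA as two successive rises from nadir at least 4 weeks apart, and states that this "will be used to trigger additional imaging (CT) between these time points". It adds no further condition.

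Section 8.3.4 and the synopsis (Follow up) define a rise in the same way and then qualify it: "If the overall PSA rise has a doubling time of ≥ 3 months or the PSA level has doubled" the value at trial entry, or if there is a clinical indication, restaging should be considered. Section 8.3.4 names bone and CT scans. Footnote 1 to the schedule of assessments (Section 8.8) is also permissive and names bone and CT scans.

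Section 11.2.1 defines PFS events by imaging under RECIST and adds that "for prostate cancer patients progression by bone scan and PSA progression will be considered". On the projected case mix, Section 11.1.2 says "this is estimated at 75% prostate, 14% breast and 11% lung".

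**The concern.** Two things look wrong. First, the same PSA series leads to a required scan under Section 3 and to an optional, conditional one under Section 8.3.4. Second, the doubling-time limb admits slower rises and leaves out those that double in under 3 months.

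The rule feeds the primary endpoint in the largest tumour group. Breast and NSCLC patients have CT every 3 months to month 24. Prostate patients have a 12-month gap between the month 12 and month 24 scans and no scheduled scan afterwards. The prostate control median assumed in Section 11.1.2, 18 months, falls inside that gap. An imaging-defined event there is dated by whatever scan the PSA rule produces, ordered by clinicians who know the allocation.

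**Working it through.** **Plan's own figures.** Section 11.1.2 gives 138 events and 230 patients for HR 0.75, one-sided alpha 0.20 and 80% power.

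- Schoenfeld: 4 × (0.8416 + 0.8416)² / (ln 0.75)² = 4 × 2.833 / 0.08276 = 136.9, so 137.
- Freedman: 2.833 × (1.75 / 0.25)² = 2.833 × 49 = 138.8, so 139.
- Patients: exponential PFS with medians of 16 and 20 months, 24 months of uniform accrual and 12 months of further follow-up give a mean event probability of 0.591. Then 138 / 0.591 is about 234, within 3% of 230.

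The figures reproduce, and this point does not touch them.

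**Texts side by side.**

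| | Section 3 | Section 8.3.4 |
|---|---|---|
| Definition of a rise | two successive rises from nadir, at least 4 weeks apart | same |
| Further condition | none | doubling time ≥ 3 months, or PSA doubled from entry, or clinical indication |
| Force | triggers imaging | restaging to be considered |
| Modality | CT | bone and CT |

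The synopsis agrees with Section 8.3.4 on condition and force. The texts differ on three of the four rows.

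**Direction of the inequality.** A limit of 3 months or longer is satisfied by doubling times of 3, 6 or 12 months and failed by 1 or 2 months. A fast riser must qualify through the entry-value limb or clinical discretion.

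**Time to the trigger.** The protocol gives no PSA values, so the following are assumptions: PSA rises exponentially from nadir with doubling time DT; r is nadir PSA divided by entry PSA; PSA is read every 3 months (the visit interval to month 24). Two rises then need two visits, so nothing is flagged before month 6 after nadir. The entry-value limb is reached at DT × log2(2/r). For r = 0.1, log2(20) = 4.32; for r = 0.01, log2(200) = 7.64. Example: DT 2 and r = 0.01 give 2 × 7.64 = 15.3 months, seen at the month 18 visit. The clinical-indication limb and scheduled scans are ignored.

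Month after nadir at which the rise is flagged:

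| | r = 1 or 0.5 | r = 0.1 | r = 0.01 |
|---|---|---|---|
| Section 3, any DT | 6 | 6 | 6 |
| Section 8.3.4, DT ≥ 3 | 6 | 6 | 6 |
| Section 8.3.4, DT 1 | 6 | 6 | 9 |
| Section 8.3.4, DT 2 | 6 | 9 | 18 |
| Section 8.3.4, DT 2.5 | 6 | 12 | 21 |
| Section 8.3.4, DT 2.9 | 6 | 15 | 24 |

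The largest delay relative to a slow rise is 0 months for r of 0.5 or more, 15 − 6 = 9 months for r = 0.1, and 24 − 6 = 18 months for r = 0.01.

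**Patients under the rule.** 0.75 × 230 = 172.5. With the protocol's site medians, HR 0.75 at each site and the accrual pattern above, prostate supplies about 93 of 138 events (67%).

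**The case against.** Section 3 is a design summary, and one can argue that sites work from Section 8.3.4. That does not resolve the conflict: Section 3 states its own complete rule, differing in condition, force and modality.

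The stronger objections concern size, and most of them stand.

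- **Scheduled scans.** Up to month 24 no gap exceeds 12 months, so a longer delay that begins before month 24 meets a scheduled scan. Only later rises lack this backstop.
- **Clinical indication.** This limb is open to any fast riser and can remove the delay altogether.
- **Entry PSA.** Patients may enter up to 8 weeks after a change of endocrine therapy. Entry PSA may then already be reduced, which brings r closer to 1 and shortens the delay.
- **PSA progression.** It is a separate component of PFS, so a fast rise may become an event without a triggered scan.

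A reader might infer more than the document supports. A contrast between a fast rise flagged after 15 months and a slow one flagged at once would be wrong, because both need two rises first and the 15 months belongs to a near-worst 100-fold fall in PSA. The 67% is the share of all modelled prostate events, not of events whose date would change. Nor does the protocol equate two PSA rises with PSA progression; the definition of that component may sit in the SAP, which is not shown, so its absence is not part of this point.

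**Conclusion.** The point holds as a contradiction, with a doubtful inequality, in a rule that feeds the primary endpoint. The conflict between Section 3 and Section 8.3.4 with the synopsis is plain from the text, as is the fact that the doubling-time limb is met by slow rises and not by those doubling in under 3 months. The date of an imaging-defined PFS event between or after the scheduled prostate scans can therefore depend on which section a site follows.

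The size is not fixed by the document. On the assumptions above, the added delay for a fast rise runs from 0 to about 18 months according to how far PSA falls from entry to nadir. The safeguards reduce that by an amount that cannot be calculated. The number of affected events is unknown. The 75% is itself a projection from first-year recruitment: with 270 patients and 50 in each of the other two cohorts it would be 170/270 = 63%.

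A reader might also infer bias between arms. One rule applies to both, so the documents do not show it. It is possible because restaging is discretionary in a non-blinded trial, and because an arm with deeper nadirs would reach twice the entry PSA later.

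**What to change.** Reconcile the synopsis, Section 3, Section 8.3.4 and footnote 1 of Section 8.8 to a single PSA restaging trigger. State once its condition, whether imaging is required or only considered, and which scans are meant, and say that it applies identically in both arms. Have the sponsor confirm the direction of the doubling-time inequality. Which trigger is clinically right is for the sponsor and investigators, and this review proposes none.

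The cost is amendment wording and a memo to sites. PSA is already measured at every follow-up visit, so no new assessment is needed, though some additional triggered scans are possible. Sample size and event target are unchanged.
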